6.2.4. Key Secondary Efficacy Endpoints

- Proportion of births prior to $37^{0/7}$ weeks' gestation – ascertain the GA at delivery based on a records review
 - Proportion of births at term ($37^{0/7}$ to $41^{6/7}$ weeks' gestation) – ascertain the GA at delivery based on a records review
 - Length of neonatal hospital stay – confirm duration (in days) of neonatal hospital admission from the medical records
 - Proportion of neonates with any diagnosis from the neonatal morbidity and mortality composite determined up to 28 days after EDD (of $40^{0/7}$ weeks) – proportion of infants with any one of the following:
 - Fetal or neonatal death
 - RDS
 - Requiring continuous positive airway pressure or mechanical ventilation. Diagnosis requires a chest radiograph consistent with RDS (reticulogranular appearance to the lung fields or air bronchograms) within the first 24 hours of life
- OR
- Received surfactant for a clinical picture of RDS within the first 24 hours of life

- Bronchopulmonary dysplasia at ≥ 36 weeks postmenstrual age (determined by adding chronological age to GA at delivery), defined as follows:
 - >21% supplemental oxygen requirement
 - OR
 - Use of high-flow nasal cannula at ≥ 1 L (21% oxygen)
- Necrotizing enterocolitis or isolated perforation
 - Diagnosed by radiographic evidence of Stage II or higher according to Bell's staging criteria (fixed/unchanging bowel loops, pneumatosis intestinalis, portal venous gas, pneumoperitoneum)
 - OR
 - Pneumatosis intestinalis, bowel necrosis, or perforation noted at surgery
- Sepsis based on positive blood culture with clinical features of sepsis
- Meningitis based on positive cerebrospinal fluid culture performed as part of infection workup
- Retinopathy of prematurity
 - Confirmed by an ophthalmologist based on international committee Stage 4 or 5
 - OR
 - Requiring surgical treatment with laser or other surgical intervention including cryotherapy or treatment with anti-VEGF (vascular endothelial growth factor)
- IVH
 - Grade 3 or 4 (severe IVH)
 - OR
 - Any grade of IVH with posthemorrhagic hydrocephalus requiring a shunt
- White matter injury, documented on cranial ultrasound or magnetic resonance imaging, as indicated by the following:
 - Multiple cystic lucencies in periventricular white matter (may be bilateral or unilateral, may vary in size, and be diffuse or focal in distribution)
 - OR
 - Porencephalic cyst (not including subependymal or choroid plexus cysts)
 - OR

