8.3.5.1.2. Secondary Analysis

Key Secondary Analysis

The key secondary analysis for this study includes the proportion of births prior to $37^{0/7}$ weeks' gestation, proportion of births at term ($37^{0/7}$ to $41^{6/7}$ weeks' gestation), length of neonatal hospital stay, and composite neonatal morbidity and mortality. To preserve the overall type I error rate, the key secondary analysis will be performed if and only if the null hypothesis of the primary endpoint is rejected. In addition, a sequential testing method will be used to adjust for multiplicity of the key secondary endpoints such that the type I error rate will be maintained at 5%. The sequential testing examines the

hypothesis testing in a prespecified order, i.e., the testing of the second secondary endpoint will be performed only if the first secondary endpoint is significant at 5%, and testing of the third secondary endpoint will be performed only if the first and second endpoints are significant at 5%. The exact order of sequential testing will be detailed in the RAP.

For the endpoints of neonatal composite outcome, proportion of births prior to $37^{0/7}$ weeks' gestation, and proportion of births at term ($37^{0/7}$ to $41^{6/7}$ weeks' gestation), a logistic regression model will be used for comparing retosiban with atosiban, with GA at randomization and established progesterone use (yes or no) as a covariate. The model will use a logit link function to estimate the log odds of percentage of preterm birth. The model will include terms for treatment group, established progesterone use, and GA at randomization. The number and percentage of subjects in each treatment group, the odds ratio of response rates (retosiban versus atosiban), 95% CIs for the odds ratio of response rates, and p-value will be presented. The relative risk response rates will be computed from the odds ratio.

Length of hospital stay will be log-transformed prior to analysis. Log-transformed length of hospital stay will be analyzed using an analysis of covariance adjusting for the covariate of GA at randomization and established progesterone use (yes or no). Other covariates may be added at discretion of the study statistician. The model-adjusted length of stay will be presented for each treatment group. In addition, the treatment difference between retosiban and atosiban and associated CIs and p-values will be presented.

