8.1.2. Planned Key Secondary Efficacy Statistical Analyses

Key Secondary Efficacy Statistical Analysis	
Endpoint	
	
 • Proportion of births prior to $37^{0/7}$ weeks' gestation • Proportion of births at term ($\geq 37^{0/7}$ weeks' gestation) • Length of neonatal hospital stay • Proportion of neonates with any diagnosis from the neonatal morbidity and mortality composite determined up to 28 days after EDD (of $40^{0/7}$ weeks) (details for each composite are provided in Section 11.5.4.)

To preserve the overall type I error rate, the key secondary analysis will be performed if and only if the null hypothesis of the primary endpoint is rejected. In addition, a sequential testing method will be used to adjust for multiplicity of the key secondary endpoints such that the type I error rate will be maintained at 5%. The sequential testing examines the hypothesis testing in a pre-specified order, i.e., the testing of the second secondary endpoint will be performed only if the first secondary endpoint is significant at 5%, and testing of the third secondary endpoint will be performed only if the first and second endpoints are significant at 5%.
 
Order of sequential testing is
 
 1) Length of neonatal hospital stay 2) Proportion of births prior to $37^{0/7}$ weeks' gestation and Proportion of births at term 3) Neonate composite outcome 	
Model Specification	

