	
 • For the endpoints of neonatal composite outcome, proportion of births prior to $37^{0/7}$ weeks' gestation, and proportion of births at term ($37^{0/7}$ to $41^{6/7}$ weeks' gestation), a logistic regression model will be used for comparing retosiban with atosiban, with GA at randomization and established progesterone use (yes or no) as covariates. The model will use a logit link function to estimate the log odds of percentage of preterm birth. The model will include terms for treatment group, established progesterone use, and GA at randomization. Additionally, interactions between GA at randomization and treatment and established progesterone use and treatment will also be investigated. • Length of hospital stay will be log-transformed (at base 10) prior to analysis. Log-transformed length of hospital stay will be analyzed using an analysis of covariance adjusting for the covariate of GA at randomization and established progesterone use (yes or no). Additionally, interactions between GA at randomization and treatment and established progesterone use and treatment will also be investigated. Wilcoxon rank sum test will also be performed to compare the two treatments if length of hospital stay is not log normal. • Terms fitted in the model will include: Fixed Categorical: TRT, EP and their interaction term (TRT*EP). Interaction will

Key Secondary Efficacy Statistical Analysis	
Fixed Continuous Covariates:	be included only if the interaction is statistically significant (at 0.1 level of significance). GA and interaction term (TRT*GA). Interaction will be included only if the interaction is statistically significant (at 0.1 level of significance).
Repeated:	None
SAS Code	

 Analysis of Covariance: <pre>ods output lsmeans=means diff=diffs tests3=tests; proc mixed data=xxx; class EP TRT; model log_LoS= TRT EP GA TRT*EP TRT*GA/ddfm=kr s; lsmeans TRT /pdiff cl alpha=0.05; run;</pre> Wilcoxon rand sum test: <pre>proc npar1way data=xxx Wilcoxon; class TRT; var log_LoS; ods output wilcoxontest=wtest; run;</pre> 	
Model Checking & Diagnostics	

 Refer to Appendix 9: Model Checking and Diagnostics for Statistical Analyses. 	
Model Results Presentation	

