 - Grade 3 or 4 (severe IVH)

OR

- Any grade of IVH with posthemorrhagic hydrocephalus requiring a shunt
- White matter injury, documented on cranial ultrasound or magnetic resonance imaging, as indicated by the following:
 - Multiple cystic lucencies in periventricular white matter (may be bilateral or unilateral, may vary in size, and be diffuse or focal in distribution)

OR

- Porencephalic cyst (not including subependymal or choroid plexus cysts)

OR

- Persistent ventriculomegaly, moderate to severe
- Cerebellar hemorrhage (unilateral or bilateral)

Individual Neonatal Composite Endpoint

- This will be derived for all the conditions included under the composite endpoint. For each individual condition, the variable will be 1 if the condition is satisfied, otherwise, 0.

Neonatal Composite Endpoint without RDS

- Same as the composite endpoint without the RDS condition.

Neonatal Composite Endpoint without RDS and mortality

- Same as the composite endpoint without the RDS and fetal/neonatal death conditions.

Modified Neonatal Composite Endpoint

- Same as the composite endpoint and include the all reported neonatal events. For example, a subject is considered as experience a RDS even without record of CPAP, ventilation or Surfactant. .

Calculation of Gestational Age at Birth and Proportion of Pre-term Births

- Gestational age at birth (weeks) is defined as the gestational age when the baby is born and is captured in the eCRF. If the data are missing, the GA at birth can be calculated as follows:

$$\text{GA at Birth (weeks)} = (\text{GA at Randomization} \times 7 + \text{Time to delivery}) / 7$$

GA at randomization will be converted to 1 decimal place (i.e. 30.2 weeks GA at randomization) prior the calculation.

- Proportion of births prior to $37^{0/7}$, $35^{0/7}$, $32^{0/7}$, or $28^{0/7}$ week's gestation (preterm)

Subjects are considered to have delivered prior to $37^{0/7}$ weeks if the gestational age at birth is less than $37^{0/7}$ weeks (e.g.: < 37.0 weeks). Other proportions also will be calculated in a similar fashion. For proportion of births prior to $32^{0/7}$ and $28^{0/7}$ week's gestation, only mothers who were randomized prior to $32^{0/7}$ and $28^{0/7}$ week's gestation will be included respectively.

- Proportion of births at term ($\geq 37^{0/7}$ week's gestation)

Subjects are considered to have delivered at term if the gestational age is $\geq 37^{0/7}$ (e.g., ≥ 37.0 weeks)

Calculation of Neonatal Hospital Admission

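### The SAP gives two definitions of births at term; the one it derives has no upper limit, departs from the protocol undeclared, and is the exact complement of births before 37 weeks

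*SAP*

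**What the plan says.** Protocol Section 6.2.4 lists the endpoint as "Proportion of births at term ($37^{0/7}$ to $41^{6/7}$ weeks' gestation) – ascertain the GA at delivery based on a records review". Protocol Section 8.3.5.1.2 names it beside births before 37 0/7 weeks as a separate key secondary analysis: "proportion of births at term ($37^{0/7}$ to $41^{6/7}$ weeks' gestation), length of neonatal hospital stay, and composite neonatal morbidity and mortality". The Protocol Summary uses the same two-sided window.

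The SAP is divided:

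- **Window kept (37 0/7 to 41 6/7):** the synopsis (Section 1), the endpoint table (Section 2.2), Table 4 (Section 8.1.1) and the Model Specification in Section 8.1.2.
- **No upper limit:** the endpoint list in Section 8.1.2, "Proportion of births at term ($\geq 37^{0/7}$ weeks' gestation", and the derivation in Section 11.5.4, where "Subjects are considered to have delivered at term if the gestational age is" 37 0/7 weeks or more. The heading of Section 11.7.3 (missing data) makes the same split, below 37 versus 37 and above.

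Section 11.5.4 derives the companion endpoint from the same gestational age at birth: "Subjects are considered to have delivered prior to $37^{0/7}$ weeks if the gestational age at birth is less than $37^{0/7}$ weeks". Section 8.1.2 places both birth proportions together at step 2 of the testing order. Section 9, which lists the changes from the protocol analyses, does not mention the definition of term.

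**The concern.** Section 11.5.4 is the text a programmer follows, so its rule is the one likely to reach the tables. Under it, two endpoints that the protocol lists separately become one outcome and its mirror image. The upper limit is the only thing that distinguishes births at term from the complement of births before 37 weeks. Without it, a birth at 42 0/7 weeks or later is recorded as a term birth, which the protocol definition excludes.

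Two things are at stake: whether the reported endpoint is the protocol's, and whether a reader of the report takes two concordant key secondary results as separate support when there is only one. Section 8.1.2 also gives both definitions within the same section, so without a correction the choice falls to whoever writes the code.

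**Working it through.** The plan states no figure to reproduce here. The check is of definitions, followed by an illustration.

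**Inputs**

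- One variable, gestational age at birth (GA), serves both endpoints (SAP 11.5.4).
- One population, Maternal ITT, and one table, 2.181, report both (SAP 11.11.3). Only the 32- and 28-week proportions restrict the denominator (SAP 11.5.4).
- Covariates, the interaction rule and the handling of missing delivery dates are common to both (SAP 8.1.2 and 11.7.3).
- 97 women were randomized 1:1 (SAP 2.3).

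**Step 1: the derivation as written.** Let P = 1 if GA < 37 0/7 and T = 1 if GA ≥ 37 0/7. Then T = 1 − P for every woman, and logit Pr(T = 1) = −logit Pr(P = 1). The treatment coefficient changes sign and keeps its standard error. The odds ratio becomes its reciprocal and the p-value is unchanged.

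**Step 2: the protocol window.** Let W = 1 if 37 0/7 ≤ GA < 42 0/7. Then W = 1 − P − L, where L = 1 if GA ≥ 42 0/7. The two definitions of term therefore differ by exactly k = ΣL, the number of births at 42 0/7 weeks or later.

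**Step 3: size of k.** The documents give no count. If 0 to 3% of births are assumed to be post-term, k runs from 0 to 0.03 × 97 = 2.9, so 0 to 3 women. With about 97 / 2 = 48.5 women per arm, each such birth moves that arm's term proportion by about 1 / 48.5 = 2.1 percentage points. The Maternal ITT population leaves out women who were never dosed, so the denominator may be somewhat smaller.

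**Step 4: illustration.** In one invented data set of 97 women, logistic models with treatment, GA at randomization and progesterone use gave the following. These are not trial results.

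| Outcome | Events | Odds ratio | p | Crude relative risk |
|---|---|---|---|---|
| GA < 37 | 57 | 0.499 | 0.1005 | 0.742 |
| GA ≥ 37 | 40 | 2.003 | 0.1005 | 1.531 |

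The events sum to 57 + 40 = 97 and the odds ratios multiply to 1.000. The relative risks do not mirror each other (0.742 × 1.531 = 1.137), so that display alone differs.

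Next, k of the 40 later births were moved beyond 42 weeks at random (200 draws for each k) and the protocol window was applied:

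| k | Odds ratio range | p range |
|---|---|---|
| 0 | 2.00 | 0.10 |
| 1 | 1.83 to 2.22 | 0.06 to 0.16 |
| 2 | 1.68 to 2.46 | 0.04 to 0.23 |
| 3 | 1.54 to 2.73 | 0.02 to 0.31 |

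The spread depends on which births are post-term, and in which arm. At k = 0 the two definitions give the same result.

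**The case against.** The strongest reply is that the redundancy comes mostly from the protocol. Even with the window restored, the two endpoints differ only by post-term births, and if there are none the correction changes no number. That stands, and it limits the size of the point.

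The SAP also treats the pair largely as one dichotomy: one step in the testing order, one missing-data section, one output table. A careful reader may therefore not count them twice. That is fair, but the protocol lists them as two key secondary endpoints, and nothing in the SAP says that one has become the complement of the other.

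Two stronger readings are tempting, and the documents do not support them.

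- A reader might infer that the SAP as a whole abandons the protocol endpoint, so that it is never analysed. Four places in the SAP keep the window, and the Section 8.1.2 model text commits to a logistic regression on it. What the documents show is a contradiction, with the derivation on the wrong side.
- A reader might infer that pairing the two at step 2 inflates type I error. Two identical tests reject together or not at all, so they add no error. SAP Section 5.2 also withdraws multiplicity adjustment because of early termination; its conflict with the sequence still printed in Section 8.1.2 is a separate matter.

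**Conclusion.** The point holds as an undeclared inconsistency in the definition of a key secondary endpoint. Followed literally, Section 11.5.4 yields something other than the protocol's births at term: an exact complement of births before 37 weeks, with post-term births counted as term.

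The complement result is exact. It rests only on both endpoints using the same gestational age variable, population and model, as the SAP specifies. The numerical consequence is bounded by the count of births at 42 0/7 weeks or later. That count is unknown and possibly zero; the figure of 0 to 3 women rests on the assumed 0 to 3%. Early termination does not explain the change, since a smaller sample gives no reason to remove an upper limit. The correction is worth making because it is nearly free and settles which endpoint is reported, not because it is likely to alter the trial's conclusion.

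**What to change.** In the SAP Section 8.1.2 endpoint list and in Section 11.5.4, define births at term as gestational age at birth of at least 37 0/7 and less than 42 0/7 weeks, with births at 42 0/7 or later counted as non-term. Align the Section 11.7.3 heading. The cost is two definitions, one heading and one line of derivation code.

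If the sponsor prefers 37 0/7 weeks or more, align the synopsis, Section 2.2, Table 4 and the Section 8.1.2 model text, and declare the change in Section 9. Report the endpoint as the complement of births before 37 weeks, not as a separate key secondary test. Deleting it without a declaration would itself be an undeclared departure from the protocol.

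Either choice should be recorded before database freeze, since the SAP synopsis says that decisions on the final analyses are made before then.

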3.1.6. Neonatal Medical Record Review Phase

Newborns will be followed in this study through 28 days post EDD as outlined in [Table 5](#). For infants who are still hospitalized 28 days post EDD, no further data will be collected as part of this study. Data after 28 days post EDD may be captured as part of a separate infant follow-up study.

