3. PLANNED ANALYSES

All planned analyses will be done using SAS version 9.2 or higher. The Analysis Data Model (ADaM) will be created per ADaM implementation guide version 1.1. Details on

derivation of variables will be specified in the specification document of ADaM. All analysis tables, listings and figures will be generated based on ADaM and/or Study Data Tabulation Model (SDTM).

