
 For binary endpoints, the number and percentage of subjects in each treatment group, the relative risk (RR) and 95% CIs, the odds ratio (OR) of response rates (retosiban versus atosiban) and 95% CIs, and p-value will be presented. The model-adjusted length of stay will be presented for each treatment group. In addition, the treatment difference between retosiban and atosiban and associated 95% CIs and p-values will be presented. Observed values using descriptive statistics for length of stay will be presented for each treatment group. For proportion of neonates with any of the composite component, neonates with any of the composite component w/o RDS, neonates with any of the composite component w/o RDS and mortality, and individual composite component, RR and 95% CIs, OR and 95% CIs, and p-values will be provided. 	
Sensitivity and Support Statistical Analysis	

 For length of stay, data will be analyzed in a similar fashion as described in Section 7.1.2. 	

Key Secondary Efficacy Statistical Analysis

- Treatment effects within defined subgroups in Section 5.1 will be explored.

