- For the delivery visit hospitalization, the length of the hospital stay (days) and associated hospital unit (NICU, nursery level, or level of care 1 to 4) will be recorded. The length of stay is calculated as the days between the delivery date/time and discharge date/time.
- In addition, whether the baby was transported to a different hospital or extended stay facility and length of stay (days) and number of hospital readmissions in the month following discharge from the delivery visit hospitalization will also be captured and reported.

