11.7.4. Length of Hospital Stay

The handling of missing data in neonatal hospital length of stay can be summarized as follows.

Length of hospital stay will be log-transformed (at base 10) and checked for normality prior to analysis. If the normality assumption holds, the missing values in the length of hospital stay will be multiple imputed and then analyzed using an analysis of covariance adjusting for the covariate of GA at entry and established progesterone use (yes or no). If the normality assumption is violated, the missing values will not be imputed and Wilcoxon rank sum test will be performed to compare the two treatments with all observed data.

If the length of stay data is log-normally distributed, the missing data (in log scale) will be imputed using the SAS® MI procedure with the regression method. The model includes treatment (TRT) and GA at birth (GA_birth) as predictors, where GA at birth is considered complete with missing values (if any) being imputed with the last contact date or last record available in the study database. The missing data will be filled in 1000 times to generate 1000 complete data sets. Sample SAS® code of the procedure can be found in below:

```
proc mi data=dsetin seed=xxx out=dsetmi n impute=1000;
  class TRT;
  monotone regression;
  var TRT GA_birth log_length_stay;
run;
```

Once the 1000 completed datasets are produced, analysis of the log-transformed length of hospital stay will be repeated on these imputed datasets, using a regression model to estimate the effect of treatment adjusting for GA at randomization (GA_rand) as continuous covariate and established progesterone use (EPU) as categorical covariate:

```
proc mixed DATA=dsetmi;
  class TRT EPU ;
  model log_length_stay = TRT GA_rand EPU / solution cl;
  lsmeans trtmt / cl diff;
  by _Imputation_;
```

```
ods output diffss=lgdiffs SolutionF=parameters CovB=covb;  
run;
```

PROC MIANALYZE will then be used to combine the results of analyses on the multiply imputed datasets based on Rubin's combination rules (Rubin, 1987):

```
proc mianalyze data=lgdiffs;  
  modeleffects estimate;  
  stderr stderr;  
  ods output PARAMETERESTIMATES=diffs_mi;  
run;
```

The combined results will be back transformed to normal scale afterwards.

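### If left blank, a neonatal stay still running at 28 days post EDD is imputed or dropped although its minimum is known, and no stay value is set for a death before discharge

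*SAP*

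**What the plan says.** Length of neonatal hospital stay is a key secondary endpoint. SAP 11.5.4 defines it: "The length of stay is calculated as the days between the delivery date/time and discharge date/time".

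Follow-up stops at a fixed date. Protocol 3.1.6 states: "For infants who are still hospitalized 28 days post EDD, no further data will be collected as part of this study". Protocol 6.2.2 repeats this, and adds that later data may be captured in the separate infant follow-up study.

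SAP 11.6.2 treats a blank field as missing. For missing stays SAP 11.7.4 has two branches:

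- If log10 stay is normal, "the missing values in the length of hospital stay will be multiple imputed and then analyzed using an analysis of covariance". For the imputation, "The model includes treatment (TRT) and GA at birth (GA_birth) as predictors"; neither the text nor the sample code sets a lower limit.
- If it is not normal, "the missing values will not be imputed and Wilcoxon rank sum test will be performed to compare the two treatments with all observed data".

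SAP 8.1.2 describes the second branch differently: "Wilcoxon rank sum test will also be performed to compare the two treatments if length of hospital stay is not log normal". It also says that "the treatment difference between retosiban and atosiban and associated 95% CIs and p-values will be presented". The analysis is kept after early termination as Table 2.301 (SAP 11.11.3).

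No passage in SAP 8.1.2, 11.5.4 or 11.7.4, or in Protocol 6.2.4 or 8.3.5.1.2, gives a stay value for an infant who dies before discharge.

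**The concern.** An infant in hospital at the cut-off has a stay that is partly known: it is at least the time from birth to that date. A rule that sees only a blank discharge date loses this. The blank also depends on the outcome, because it arises when the stay is long, so the longest stays are either removed or replaced by values modelled on infants who went home earlier.

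The gap on deaths is separate. Depending on how the form is completed, a death could enter as a short stay, be imputed as a survivor's stay, or be left out. If deaths differ by arm, the first of these makes the arm with more deaths look better on stay.

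At stake are one estimate, its confidence interval and its p-value. Deaths themselves are visible elsewhere, in the neonatal composite and the neonatal deaths listing.

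**Working it through.** **1. Known minimum stay.** EDD is 40w0d for every subject (Protocol 3.1), so 28 days post EDD is 40 + 4 = 44w0d. For birth at g weeks the minimum is (44 − g) × 7 days:

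| GA at birth | Minimum stay |
|---|---|
| 25 weeks | 19 × 7 = 133 days |
| 28 weeks | 16 × 7 = 112 days |
| 32 weeks | 12 × 7 = 84 days |

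This step needs no assumption. The documents give no expected stay, SD or number of infants affected, so there is no figure of theirs to reproduce and everything below is illustrative.

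**2. What imputation does.** Every discharged infant used to fit the model left by the limit for its own GA. Assume discharge centred at 37 weeks postmenstrual age, log10 SD 0.15, and GA at birth uniform from 24 to 37 weeks. For infants still in hospital, the geometric mean true stay is then 140 days, the known minimum 120 and the imputed stay 76. Across the assumptions tried (discharge centred at 36 to 40 weeks), 54% to 92% of imputed values fall below the known minimum.

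**3. Which branch runs.** The SAP names no normality test. With Shapiro-Wilk at 5% assumed, log10 stay failed in 60% to over 99% of simulated trials. So the usual outcome is that the stay is dropped, not imputed.

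**4. Long stays alone.** The simulation used 48 per arm (97 enrolled; 97/2 = 48.5), with GA strata 1:2:4:8 and 55% delivering within 3 weeks (Protocol 8.2.1). All other inputs are assumed. With long stays in 2.7% v 5.3% (0.027 × 48 = 1.3 v 0.053 × 48 = 2.5 infants), the arm with more of them is significantly favoured in 2.9% to 4.4% of trials, against a nominal 2.5%. Using the known minimum gives 1.5% to 2.9%. Monte Carlo SE is about 0.3 to 0.6 points.

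**5. Deaths: direction.** In an arm of 48 with geometric mean stay m, one death entered as a stay of d days multiplies that mean by (d/m)^(1/48).

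- Death on day 1, m = 20: (1/20)^(1/48) = 0.939, a fall of 6.1%.
- Death on day 3, m = 10: (3/10)^(1/48) = 0.975, a fall of 2.5%.
- The same death entered as 112 days: (112/20)^(1/48) = 1.037 or (112/10)^(1/48) = 1.052, a rise of 3.7% or 5.2%.

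The coding choice decides the sign.

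**6. Deaths: effect on the test.** Share of trials that significantly favour the arm with more deaths (nominal 2.5%), with no other difference in stay:

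| Assumed deaths | Date of death as discharge | Deaths blank | Deaths ranked worst |
|---|---|---|---|
| 3% v 8% (1.4 v 3.8 infants) | 5.6–9.0% | 3.5–4.8% | 1.3–2.1% |
| 1.5% v 4.5% | 3.7–4.9% | 3.0–3.5% | 2.0% |

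With equal deaths the share is 2.2% to 2.8%.

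**7. Passages side by side.** For neonatal adverse-event end dates, SAP 11.6.2.2 sets both a death-date rule and a 28-days-after-EDD rule. It sets neither for stay. Separately, SAP 8.1.2 adds the Wilcoxon test to the ANCOVA, while 11.7.4 uses it in place of the ANCOVA and without imputation.

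**The case against.** No sentence says that an infant still in hospital is treated as missing. That follows only if the discharge field is blank. SAP 11.6.2 says that entries such as Not applicable are not missing data, and 11.7.4 would not reach those. SAP 3 also says that "derivation of variables will be specified in the specification document of ADaM", and that document is not available here. This stands, and it is why the point is worded conditionally. But a Not applicable entry would leave the stay undefined, which is still a gap, and an unseen specification does not remove the written rule for blanks.

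The numbers are also open to challenge. Long stays alone move the test little. Values imputed below the minimum belong to a branch seldom reached in simulation. The death results need unequal mortality that no passage predicts, and the largest also need the date of death to be entered as a discharge, which no passage states. The 48 per arm is a maximum, since women never dosed are excluded from the ITT population. All of this stands.

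Finally, the p-value carries limited weight. SAP 5.2 drops multiplicity adjustment after early termination, yet 8.1.2 still tests key secondaries only if the primary null is rejected. If that gate applies, the error rates above are not the operating rates.

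**Conclusion.** The point holds in conditional form. A blank stay at the cut-off is imputed without a floor or left out, although its minimum follows from the documents' own dates. There is no stay rule for death before discharge, and two SAP sections conflict on the Wilcoxon test. These conclusions rest on the text alone; every error rate rests on assumed mortality and stay distributions.

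The number of infants affected at the cut-off is probably small, and so is the effect on the test. For deaths, bias needs a difference between arms.

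A reader might infer more, and the documents do not support it:

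- That the SAP declares these infants missing. It does not; this depends on how the form is completed.
- That most imputed values falling below the minimum distorts the result. That branch is unlikely to run.
- That the SAP counts a death as a short stay. It is silent on deaths.
- That the comparison is biased as planned. With equal deaths it is not.

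The rules should be settled before unblinding. The issue is confined to the stay estimate and its p-value.

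**What to change.** Before unblinding, in SAP 11.5.4 and 11.7.4:

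1. For infants in hospital at 28 days post EDD, take birth to that date as the minimum stay. Rank it as at least that long in the Wilcoxon test, and use it as the lower limit for imputed values in the ANCOVA branch, since ANCOVA cannot take a censored value directly. Limit unbounded imputation to infants whose discharge status is unknown.
2. Do not enter the date of death as a discharge, and do not impute deaths as survivors' stays. Label the main analysis as conditional on survival, show deaths by arm beside Table 2.301, and add one rank sensitivity analysis with deaths ranked worst.
3. State in both 8.1.2 and 11.7.4 whether the Wilcoxon test is added to the ANCOVA or replaces it.

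The cost is SAP wording, a short derivation and one extra analysis. Dates of birth, death and EDD are already used in SAP 11.6.2.2. The downside is that the survivors-only main test remains selected and is not improved for deaths. At the assumed 3% v 8% it favours the worse arm in 4.0% to 5.0% of simulated trials, no better than the present rule with deaths blank (3.5% to 4.8%). That is why deaths by arm and the sensitivity analysis must stand beside it. Ranking deaths worst is one choice of estimand among several, so it is proposed as a sensitivity analysis only.
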